5.8. Total expected duration of the clinical investigation

The dates below are approximate, and no subjects will be enrolled before all required approvals have been obtained. If changes are required, applicable EC and regulatory authorities will be notified.

- First subject enrolled (03/2020).
- Last subject enrolled (05/2020).
- Last subject completed (06/2020).
- Final report (10/2020).

6. Clinical Investigation population

The clinical investigation will be conducted in 12 subjects enrolled in a clinical facility at Coloplast A/S, XXXXXXXXXX

6.1. Eligibility criteria

Subjects interested in participating the clinical investigation must comply with the following criteria:

6.1.1. Inclusion and exclusion criteria

Below, in Table 1 and Table 2 inclusion and exclusion criteria are presented.

Table 1: Inclusion criteria

Inclusion criteria		Justification for inclusion criteria
To be included in the investigation a subject must comply with the following inclusion criteria:		
1.	Has given written informed consent	To ensure that the subject has been given written and oral information regarding the investigation, and know enough about the investigation to decide participation
2.	Be at least 18 years of age and have full legal capacity	To meet the Helsinki declaration
3.	Have had a stoma for more than 1/2 year	To ensure subjects are recovered from ostomy surgery
4.	Have intact skin on the area used in the study (Assessed by investigator, see Appendix 1).	The skin has to be intact in order to explore the peristomal skin after use of ostomy tape
5.	Willing to change baseplate every second day or less frequent	To ensure at least two days wear time and baseplates cannot be changed without changing the tapes

Inclusion criteria		Justification for inclusion criteria
To be included in the investigation a subject must comply with the following inclusion criteria:		
6.	Willing to avoid using Concave baseplate during the study.	The ostomy tape is not designed for this type of baseplate
7.	Willing to avoid the use of barrier creams or similar that affect the skin/adhesive interface under the tape.	Barrier creams may interfere with the study endpoints by interfering with the performance of the ostomy tapes.

Table 2: Exclusion criteria

Exclusion criteria		Justification for exclusion criteria:
A subject is not allowed to participate in case he/she:		
1.	Currently receiving or have within the past 2 months received radio-and/or chemotherapy	The skin undergoes major changes because of radio-and/or chemotherapy, and therefore, the skin might be more fragile to product changes.
2.	Currently receiving or have within the past month received topical steroid treatment in the peristomal skin area or systemic steroid (tablet(injection) treatment	Steroid product on peristomal skin may interfere with the study endpoints by making the peristomal skin thinner and more fragile.
3.	Is pregnant or breastfeeding	Even though the ingredients and the recipes have been approved for humans, their effect on embryos, foetuses, and infants are unknown.
4.	Having dermatological problems in the peristomal area (assessed by investigator)	The skin has to be intact in order to see a potential damage of the skin.

6.1.2. Pregnancy and breastfeeding

For female subjects with childbearing potential (they have had at least one period during the last 12 months), a urine pregnancy test will be performed at the inclusion visit, to ensure the subject is not pregnant. The urine pregnancy test will be performed by dipstick at the trial site. Furthermore, the female subjects should not be breastfeeding, when participating in the clinical investigation.

6.2. Recruitment and enrolment

Recruitment of potential subjects will begin once approval have been obtained from the Ethics Committee of the Capital Region Denmark and the Danish Medicines Agency.

The recruitment time is estimate to approximately 1 month.

Recruitment method	Coloplast Database
Potential subjects	
Recruitment will go through Coloplast own subject database (stoma care users) in Denmark. Potential subjects are identified by the following searching criteria in the Coloplast database:
 
 • Has an ileostomy, colostomy or urostomy • Currently not using [REDACTED] product 
Be at least 18 years of age

First contact	
The identified potential subjects will as first contact be sent an Invitation and Reply Letter by mail or email.
 
If a potential subject does not return the reply letter or answer the email, they may be contacted by phone, mail or email to make sure that they have received the approach.

Second contact	If potential subjects return the Reply Letter/reply to the email or have called the investigator as first contact and are interested, the Investigator or delegated site personnel will contact the subjects by phone and give a short introduction to the investigation and go over the inclusion and exclusion criteria. If the subjects do not meet the inclusion criteria or meet the exclusion criteria, this will be registered in the Subject Screening Log.
Subject Information Form	If subjects are eligible and interested in participating, then written information about the investigation (subject information) will be sent to the subjects to ensure that they are given the opportunity to read about the investigation before a possible informational visit, and so that they can prepare any possible questions they may have. Information visit V0 will be booked at this point and the subjects are instructed to contact the investigator or delegated study personnel if they, after having read the subject information, no longer are interested in participation in the study.
First visit Information visit	If an eligible subject is interested in participating, baseline visit (V0) will be arranged in a room ensuring quiet surroundings at Coloplast. When arranging the visit, it will be ensured, that the subject has received the Subject Information prior to the visit. The subjects will receive both written and verbal information about the possibility of bringing a companion to the informational visit and to any possible subsequent visits. See section 16. for information to be given to the subjects, as well as the informed consent process.
Enrolment and Baseline visit (V0)	The subjects have the right to wait 24h before deciding on participation. If/when the subject decides to participate he/she will be asked to sign the relevant forms (see section 16). If a subject so desires, and it is certain that it is understood what the investigation entails, and the relevant forms have been signed the subjects are considered enrolled in the investigation.

6.3. Subject withdrawal criteria

The subject is allowed to withdraw from the investigation at any time for whatever reason without any consequences for their future treatment outside the clinical investigation. The Investigator may withdraw a subject from the investigation at any time if they judge it to be the subject's interest.

The investigator must withdraw a subject from the investigation due to:

- Noncompliance with the CIP impacting the scientific integrity of the investigation.
- If subject's safety and wellbeing is compromised by further participation.

Subjects lost to follow-up. At least three documented attempts will be made to verify subjects lost to follow-up.

Withdrawn subjects will not be replaced by new subjects.

A subject who is withdrawn from the investigation, for any reason, will be encouraged to contact the investigator if problems arise that the subject believes are related to the clinical investigation. Subjects who have not experienced any adverse events will not be followed up. For subjects who experience adverse events, see section 17.

6.4. Point of enrolment

A subject is considered enrolled in the investigation when the written informed consent is obtained. The expected duration for each subject is described in section 5.1

6.5. Subject Identification and Confidentiality

Subjects will be identified on the electronic CRF (e-CRF) and any other document transmitted to the sponsor by the principal investigator or clinical site staff, by a unique identification number.

Data entered on the e-CRF are confidential and will only be available to the sponsor (including sponsor delegates), members of data management teams, the statistician, and members of the EC or regulatory authorities if requested.

The principal investigator for each clinical investigation site will maintain as part of the investigational file a list identifying all subjects entered into the clinical investigation.

7. Procedures

7.1. Clinical investigation-related procedures

Before initiation of the clinical investigation, sponsor must be provided with key personnel signed and dated curriculum vitae (not more than 2 years old) to verify their qualifications. Key site personnel are those, who treat or evaluate subject data in the clinical investigation. Also, the sponsor will ensure that all site personnel are trained in the investigation procedures, how to complete the CRFs, procedure for reporting an adverse event or serious adverse event (how, when, to whom), and who to contact in case of emergency related to the investigational device.

See section 7.3 Flow-charts for a more detailed overview of the clinical investigation-related procedures at visits.

7.2. Visits

Baseline visit (V0):

- Introduction to the study
- Informed Consent and letter of authority signed
- Check of in- and exclusion criteria
- Visual evaluation of skin for inclusion
- Pregnancy test - dipstick (for women of child-bearing potential only)
- Inclusion in study and allocation of subject number
- Collect baseline information
- Possibility to accept interview by User Insight/development engineers/project members

Test visit 1:

- Randomisation
- Instruct subject in use of smartphone and Clinical Trial app and remind the subject to bring it for every study visit
- Remove tape/product with use of adhesive remover
- Photo of peristomal skin (digital camera)
- Acclimatization of peristomal skin for ½ hour
- Photo of peristomal skin after acclimatization (digital camera)
- Measurements of erythema
- Provide randomized test products or comparator products for the subject for change at home and apply 2 ostomy tapes on the peristomal skin (after ostomy product has been applied).
- Provide storage material for used ostomy tapes and adhesive remover
- Instruct and remind the subject to follow the study specific procedures between visits
- Schedule next visit in 7-9 days

Test visit 2 and 3:

- Follow up on subjects use of smartphone and Clinical Trial app and remind the subject to bring it for every study visit
- Ostomy tapes are removed with use of adhesive remover (before removing, mark the lifted tape area with a pen on the adhesive part)
- Photo of peristomal skin (digital camera)
- Photo of skin (smartphone – Clinical Trial App)
- Smartphone: Questionnaire about feeling of security, adhesion of tape, comfort & skin issues in the area covered by the tape
- Acclimatization of peristomal skin for ½ hour
- Photo of peristomal skin after acclimatization (digital camera)
- Measurements of erythema

- Provide randomized test products or comparator products for the subject for change at home and apply 2 ostomy tapes on the peristomal skin (after ostomy product has been applied).
- Provide storage material for used ostomy tapes and adhesive remover
- Instruct and remind the subject to follow the study specific procedures between visits
- Schedule next visit in 7-9 days
- Collect all used tapes and measure the adherent area
- Review AEs/ADEs/SAEs/SADEs
- Possibility to accept interview by User Insight/development engineers/project members

Termination visit 4:

- Follow up on subjects use of smartphone and Clinical Trial app
- Ostomy tapes are removed with use of adhesive remover (before removing, mark the lifted tape area with a pen on the adhesive part)
- Photo of peristomal skin (digital camera)
- Photo of skin (smartphone – Clinical Trial App)
- Smartphone: Questionnaire about feeling of security, adhesion of tape, comfort & skin issues in the area covered by the tape
- Acclimatization of peristomal skin for ½ hour
- Photo of peristomal skin after acclimatization (digital camera)
- Measurements of erythema
- Application of stoma product which subject normally use
- Collect all used tapes and measure the adherent area
- Review AEs/ADEs/SAEs/SADEs
- Collect smartphone
- Possibility to accept interview by User Insight/development engineers/project members
- Fill in termination form

Product change and study specific procedures, to be followed at home:

Between visits the subject will change at home. At each product change, the subject should record experience at home by taking photo of the peristomal skin and answer questionnaires (with a Clinical Trial app on a handed-out smartphone).

At home:

- a) Remove tape with use of adhesive remover (before removing mark the lifted tape area with a pen on the adhesive part).
- b) Remove the tape from baseplate and save the tapes in the provided storage material for the next visit
- c) Take photo of peristomal skin.
- d) Answer questions (about feeling of security, adhesion of tape, comfort & skin issues in the area covered by the tape)

7.3. Flow-chart

Table 3 chart showing the connection between visits and assessments.

	PERFORMED BY	BASELINE	TEST PERIOD	TEST PERIOD	TEST PERIOD	TERMINATION
VISIT WINDOW (DAYS)	-	-	-	7 - 9	7 - 9	7 - 9
GENERAL						
Subject information	Investigator	X				
Signed informed consent	Subject / Investigator	X				
Signed letter of authority	Subject / Investigator	X				

Allocation of subject number	Investigator	X				
Check of in- and exclusion criteria	Investigator	X				
Visual evaluation of skin for inclusion	Investigator	X				
Pregnancy test, dipstick (If applicable)	Investigator	X				
Randomization	Investigator		X			
Insurance of subjects' wellbeing and compliance with CIP	Investigator	X	X	X	X	X
COLLECTION AND REGISTRATION OF BASELINE DATA						
Demographics: Gender, age, height and weight	Investigator	X				
Stoma: Type, reason and duration	Investigator	X				
Use of ostomy tape (Y/N)	Investigator	X				
Use of other accessories (Ring and paste)	Investigator	X				
Usually stoma product used	Investigator	X				
Optionally interviews	Development engineers/project members			X	X	X
PROCEDURES						
Instruct in and follow up on subjects use of smartphone and Clinical Trial app	Investigator		X	X	X	X
Remind the subject to bring the smartphone at every study visit	Investigator		X	X	X	X
Mark the lifted tape area with a pen on the adhesive part, before removing the ostomy tapes	Investigator			X	X	X
Remove tape/product with use of adhesive remover.	Investigator		X	X	X	X
Photo of peristomal skin (digital camera)	Investigator		X	X	X	X
Photo of peristomal skin (smartphone)	Subject			X	X	X
Acclimatize peristomal skin for ½ hour	Subject		X	X	X	X
Smartphone, Questionnaire: Feeling of security, adhesion of tape and comfort	Subject			X	X	X
Smartphone, Questionnaire: Skin issues in the area covered by the tape	Subject			X	X	X
Photo of peristomal skin, after ½ hour acclimatization (digital camera)	Investigator		X	X	X	X
Measure erythema	Investigator		X	X	X	X
Provide test products to the subject	Investigator		X	X	X	
Apply ostomy product and ostomy test tapes (Test tapes should be applied at the edges of the baseplate)	Subject		X	X	X	
Provide storage material for used ostomy tapes and adhesive remover	Investigator		X	X	X	
Instruct and remind the subject to follow the study specific procedures between visits	Investigator		X	X	X	X

Schedule next visit	Investigator	X	X	X	X	
Collect all used tapes and measure the adherent area by photography	Investigator			X	X	X
Registration of AEs/ADEs/SAEs/SADEs	Investigator		X	X	X	X
Complete eCRF	Investigator	X	X	X	X	X
REGISTRATION OF TERMINATION						
Termination form	Investigator					X

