1.2. Investigators

The Clinical Manager is responsible for maintaining an updated list of all PIs, investigation sites and institutions.

PRINCIPAL INVESTIGATOR
[name]
[REDACTED]

2. Rational/justification for conducting the clinical investigation

People with abdominal stomas have, despite development of better ostomy products, still problems with leakage and peristomal skin disorders which influence their quality of life negatively [1,2].

To minimize the risk of leakage on clothing, ostomy tape can be used. [REDACTED] and is used to support the rim of the ostomy base plate/adhesive by providing additional adhesion to the intact peristomal skin.

The adhesives in the ostomy tapes are developed to make the tape seal to the skin and thereby minimise the risk of leakage episodes. At the same time, the tape should be easy to remove without affecting the skin.

This evaluation investigates two newly developed adhesives and their ability to adhere to the skin without affecting it. Based on the knowledge obtained in this investigation, an improved ostomy tape can be developed and thereby give ostomists new supporting products that reduce the risk of leakage episodes.

3. Objective(s) of the clinical investigation

The purpose of the study is to explore different recipes of ostomy tapes and understand their ability to adhere to the skin without affecting it.

The primary objective is to explore the adherent area after use.

Secondary objective is to explore the skin after application of the ostomy tapes.

4. Investigational device and comparator(s)

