5.1. General

This investigation is a randomised, open-label, comparative, cross-over study, with three test periods.

In total, 12 subjects will be included and randomised, and each subject will have an inclusion visit and four test visits overseen by the Principal Investigator, or delegate. Each subject will be enrolled for three times 7-9 days in total for the entire investigation, thus for a maximum of 27 days – equal to at least 3 baseplates + tape change in each period. The subjects will test two new recipes of ostomy tapes and a comparator product in randomised order.

Between the test visits, the subjects will change products at home. At each product change, subjects will take a photo of the peristomal skin using a smartphone with a specially designed Clinical Trial app installed. Furthermore, they will answer questions about feeling of security, adhesion of tape, comfort and potential skin issues.

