5.3. Secondary endpoints

- Erythema measured after each treatment period by spectrophotometric method
- Erythema measured after tape removal by photos
- Feeling of security:
 - How was the feeling of security while wearing the tape?
(5-point scale from Very poor to Very good)
 - Did you feel confident that the tape would keep your base plate securely in place?
(5-point scale from Very little to Very much)
- Adhesion of tape:
 - How was the immediate adhesion to the skin?
(5-point scale from Very poor to Very good)
 - Did the edge of the tape lift/roll during use?
(5-point scale from Very poor to Very good)
- Comfort:
 - How comfortable was the tape to wear?
(5-point scale from Very uncomfortable to Very comfortable)
 - Did the tape allow you freedom of movement?
(5-point scale from Very little to Very much)
- Skin issues in the area covered by the tape:
 - Do you experience any **bleeding from the skin** under the tape right now when changing your product? (Experiencing/Not experiencing)
 - Once you have cleaned and dried the skin, do you experience any **weeping or moisture on the skin** under the tape right now when changing your product? (Experiencing/Not experiencing)
 - Are you experiencing any **ulcers or sores** under the tape right now when changing your product? (Experiencing/Not experiencing)
 - Did you experience complications where the tape was applied (like pain, stinging, itching, heat swelling or shiny skin)? (Yes/No)

- Please rate how painful the skin under the tape has been at its worst, since you last changed your product. (10-point scale from no pain (1) to worst pain possible (10))
- Please rate how itchy the skin under the tape has been at its worst, since you last changed your product. (10-point scale from no itch to worst itch possible)
- Adverse events

User experience with feeling of security, adhesion of tape, comfort and skin issues in the area covered by tape, will be assessed by prior mentioned questionnaires which will be assessed by interviews at Coloplast visit and self-reported by user at home.

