Injured skin can be distinguished in two levels, depending on the depth of the above-mentioned changes:

- 1) Intact injured skin (superficially injured skin): skin which presents with superficial pathological changes or changes following disease or trauma but where the basement membrane is unbroken. Skin changes of this kind are expected to heal with no permanent damage or scarring to the skin [3]
- 2) Non-intact injured skin: skin which present with pathological changes or changes following disease or trauma and where the basement membrane is breached. Healing is by secondary intend (if left to heal on its own) and scarring is expected [3].

2. Mucous Membrane

2.a. Intact mucous membrane

Intact mucous membrane is mucous membrane (mucosa) whose basement membrane is intact. Mucous membrane consists of epithelium, lamina propria, muscularis mucosae and sub mucosa. [2] The basement membrane is the basal part of the non-vascularized epithelium, separating it from the underlying vascularized tissues.

If the basement membrane is broken the blood vessels in the underlying tissue are exposed and the mucus membrane is no longer considered intact.

2.b. Injured mucous membrane

Injured mucous membrane is mucous membrane presenting pathological changes or changes following disease or trauma.

Injured mucous membrane can be distinguished in two levels, depending on the depth of the above-mentioned changes:

- 1) Intact injured mucous membrane (superficially injured mucous membrane): mucous membrane which presents with superficial pathological changes or changes following disease or trauma but where the basement membrane is unbroken. Mucous membrane changes of this kind are expected to heal with no permanent damage or scarring to the mucosa [4].
- 2) Non-intact injured mucous membrane: mucous membrane which presents with pathological changes or changes following disease or trauma and where the basement membrane is breached.

References

1. Regulation (EU) 2017/745 of the European parliament and of the council of 5 April 2017 on Medical devices, <http://eur-lex.europa.eu/legal-content/ENG/TXT/PDF/?uri=CELEX:32017R0745&from=EN>
2. Gray's Anatomy, 40th Edition. The Anatomical Basis of Clinical Practice. Susan Standring. Ed. Churchill Livingstone, 25th September 2008
3. Madeleine Flanagan: Wound Healing and Skin Integrity, 2013, page 34, re to Enoch and Leaper 2005

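### The self-reported skin items are first collected after a study tape has been worn, so pain, itch, moisture and complications have no pre-tape value

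*Combined protocol and SAP*

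**What the plan says.** Section 3 gives the purpose as exploring tape recipes and to "understand their ability to adhere to the skin without affecting it". The secondary objective concerns the skin after tape application.

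Section 5.3 lists six skin-issue items. Four are two-category: bleeding, weeping or moisture, ulcers or sores, and complications. Two are 10-point ratings, for pain and itch. All are worded for skin that has a tape on it, for example "Please rate how itchy the skin under the tape has been at its worst, since you last changed your product".

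Table 3 schedules the questionnaire ("Smartphone, Questionnaire: Skin issues in the area covered by the tape") at V2, V3 and V4 only. For home use, section 7.2 says: "At each product change, the subject should record experience at home by taking photo of the peristomal skin and answer questionnaires". At V1 the only app-related step is "Instruct subject in use of smartphone and Clinical Trial app and remind the subject to bring it for every study visit". The same visit includes camera photos and an erythema measurement, and then application of the first study tapes.

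Baseline data in section 5.5 cover demographics, stoma history, usual product, accessories and prior tape use (Y/N). They contain no symptom item. Section 10.1 plans descriptive summaries of these questions by product.

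**The concern.** The stated purpose is partly absolute: do the tapes leave the skin unaffected? A reading of the self-reported items on that question needs either a no-tape condition or a value from before the first study tape. The plan has neither.

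A person with a stoma may have some itch, soreness or moisture under the usual appliance. Section 2 itself says that peristomal skin disorders remain a problem in this population. If such a complaint continues unchanged through the study, it appears in the summary for every product. It then looks the same as a complaint that every tape provokes.

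The plan does take pre-tape values at V1 for the camera photos and the erythema reading. Redness can therefore be read against a starting point, and symptoms cannot.

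**Working it through.** The plan states no figure to reproduce, because this is a question of timing. The check sets Table 3 beside the visit lists and home procedures in section 7.2.

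**1. What exists before the first study tape.** The five visit columns of Table 3 are taken as V0 to V4.

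| Assessment | V0 | V1, before tape | First home change, period 1 | V2 to V4 |
|---|---|---|---|---|
| Skin-issue questionnaire | none | none | yes | yes |
| Digital-camera skin photo | none | 2 time points | none | yes |
| Erythema measurement | none | 1 time point | none | yes |
| Visual skin check | eligibility only | none | none | none |

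Questionnaire completions before the first study tape are therefore 0, so 0 of 6 items has a pre-tape value. Section 7.2 mentions an optional interview at V0, but gives it no content, and Table 3 marks interviews only from V2.

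**2. When the first answers arrive.** Section 5.1 gives at least 3 changes per period. If the removal at V2 is one of the 3, at least 3 − 1 = 2 home records per subject precede V2, or 2 × 12 = 24 in all. If it is not, the figure is at least 3 × 12 = 36. All of them follow wear of a study tape, so none is a baseline.

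**3. What the planned summaries can identify.** Take a pain or itch rating for subject *i* under product *p* as

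Y(i,p) = s(i) + a + d(p) + error,

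where s(i) is the subject's usual level, a is any effect common to all three tapes, and d(p) is the product-specific part, with the three d(p) summing to zero.

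- Contrast between products p and q: d(p) − d(q). Both s(i) and a cancel, so the contrast is sound.
- Mean for product p: mean of s + a + d(p). The mean of s and the common effect a cannot be separated.

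All three products are tapes. The comparator's name is blacked out, but section 7.2 applies two tapes whichever product is supplied, and section 10.1 models adherent area for all three. No period shows s(i) alone.

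**4. The same for a Yes/No item.** Suppose k of 12 subjects report a complaint. The documents give no value for k, so k is an assumption.

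| | Each product's summary | Difference between products | V1, if asked | New since V1 |
|---|---|---|---|---|
| Usual complaint, tapes cause none | k/12 | 0 | k/12 | 0 |
| No usual complaint, every tape causes it | k/12 | 0 | 0/12 | k |

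For k = 1, 2 and 3, the summary reads 8%, 17% and 25% in both rows. Only the V1 columns tell the rows apart.

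**5. Does eligibility set the starting value to zero?** Inclusion criterion 4 refers to Appendix 1, which defines intact skin by an unbroken basement membrane and recognises intact injured skin: "skin which presents with superficial pathological changes or changes following disease or trauma but where the basement membrane is unbroken". Exclusion criterion 4 narrows this by removing subjects with peristomal dermatological problems, on the investigator's judgement. With the visual check at V0, it should largely remove bleeding and sores. A visual check does not fix felt pain or itch at zero, and it records no moisture or complication answer.

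**The case against.** The strongest reply is that this is an exploratory, 12-subject cross-over with a marketed comparator. Each subject serves as their own control, stable complaints cancel in product contrasts, no change-from-baseline analysis is planned, and section 10.4 sets no pass/fail rule. That stands. A reader might infer that product comparisons are biased, or that the plan attributes usual complaints to the tapes. The documents support neither.

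A reader might also infer that redness lacks a pre-tape value because the app photo is not taken at V1. It does not lack one: the V1 camera photos and erythema reading recur at V2 to V4. The plan does not say that app photos are scored for the photo endpoint.

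Nor are all six items equally exposed, given exclusion criterion 4 and the V0 check.

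It is tempting to set an assumed symptom prevalence against the irritation rate of below 10% in section 17.2. That comparison fails. The section 17.2 figure is an anticipated rate of adverse device effects, not of questionnaire answers, and the plan gives no threshold that turns an itch rating into a case.

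Finally, a V1 answer would be an imperfect reference. It is a single snapshot, and it describes skin under the subject's own appliance, with a tape in some subjects and without in others. This also stands. It limits how the value should be reported, but one imperfect reference is still more than none.

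**Conclusion.** The point holds in a limited form and is minor: an optional improvement. The self-reported skin items, chiefly pain, itch, moisture and complications, have no value from before the first study tape. The summaries by product therefore cannot distinguish symptoms already present from symptoms common to all three tapes. The primary endpoint, the redness endpoints and the within-subject product contrasts are not affected.

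The loss matters only to the extent that subjects have usual symptoms, or that all three tapes share an effect. The documents give no figure for either, so no numerical size can be stated beyond the 0 of 6 count. The conclusion assumes that Table 3 and section 7.2 are the complete schedule of questionnaire completions.

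**What to change.** In Table 3 and in the Test visit 1 list of section 7.2, add one completion of the skin-issue questionnaire, after the subject's own product is removed and before the first study tape is applied. For this completion only, replace the reference to skin under the tape with *where the tape will be applied*, and adapt the complications item in the same way.

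In section 10.1, add that the V1 values, and the number of subjects new or worsened since V1, will be shown beside the planned summaries by product. Define new as No at V1 and Yes later. Define worsened as a higher pain or itch rating than at V1. Use the clinic-visit record that closes each period for this count, so that one answer is compared with one answer, not with the worst of three or more. Show prior tape use, already recorded at V0, alongside.

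The cost is a few minutes at V1, when the subject is already being taught the app, and one extra form version. The remaining downside is that the reference is a single value relating to the subject's own appliance, and the text should say so. In periods 2 and 3, a change since V1 may also reflect the tapes worn earlier. The planned summaries stay as they are.
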